#### **4.2 Intervention**

All enrolled patients will undergo a baseline F-FDG PET scan as part of their standard clinical treatment for NSCLC. Dynamic F-FMISO PET scans will be performed on one of the GE PET/CT scanners in 3D mode, at least one day after the baseline F-FDG PET scan. The dynamic baseline F-FMISO studies may precede the F-FDG study if the patient had a CT or PET/CT scan within the last 30 days that would permit the investigators to localize the tumor of interest during the F-FMISO study. In a group of 5 patients, the feasibility of simultaneous imaging of F-FMISO and F-FDG will be assessed. The patient will have an IV line placed for radiotracer injection and for venous blood sampling. All dynamic PET scans will be performed over one PET FOV centered at the lesion position. The F-FDG mid-treatment PET/CT scan will be performed over only one bed position at the times identified in section 1.0.

The studies outlined in Section 9.0 are the intervention. These research study results will not impact clinical care which will be left to the discretion of the treating physician. Patients will be followed with CT scans of the chest every 3-4 months in the first three years as per standard clinical care. Available data will be used for radiologic progression of disease and survival.

### **5.0 THERAPEUTIC/DIAGNOSTIC AGENTS**

F-18 labeled F-misonidazole is prepared and tested for quality assurance in this study at MSKCC or by an equivalent qualified supplier. The radiopharmaceutical is being utilized in this protocol under a MSKCC IND. Bio-distribution data on F-MISO are summarized in section 11.2.3.

### **6.0 CRITERIA FOR SUBJECT ELIGIBILITY**

#### **6.1 Subject Inclusion Criteria**

- Pathologic confirmation of NSCLC at MSKCC
- No prior treatment for this diagnosis of NSCLC
- Patient to be treated with neoadjuvant chemotherapy or patient to be treated with definitive RT, sequential chemo-RT, or concurrent chemo-RT (minimum dose of 50 Gy in 25 fractions)
- Tumor must measure  $\geq$  2cm on CT
- Age  $\geq$  18 years
- Ability to hold the breath for 10 seconds
- Karnofsky performance status  $\geq$  70%

- Women of childbearing age must have a negative blood pregnancy test

## **6.2      Subject Exclusion Criteria**

- Women who are pregnant or breast-feeding
- Severe diabetes (fasting Blood Glucose > 200 mg/dl)

## **7.0      Recruitment Plan with limited waiver of authorization**

Potential research subjects will be identified by a member of the patient's treatment team, the protocol investigator, or research team at Memorial Sloan-Kettering Cancer center (MSKCC). If the investigator is a member of the treatment team, s/he will screen their patient's medical records for suitable research study participants and discuss the study and their potential for enrolling in the research study. Potential subjects contacted by their treatment physician will be referred to the investigator/research staff of the study.

The principal investigator may also screen the medical records of patients with whom they do not have a treatment relationship for the limited purpose of identifying patients who would be eligible to enroll in the study and to record appropriate contact information in order to approach these patients regarding the possibility of enrolling in the study.

Patients who are receiving chemotherapy only will be identified when they are referred to Nuclear Medicine for their standard FDG PET scans. Patients receiving combined chemoradiotherapy will be identified by the treating Radiation Oncologist when they are assessed in the Radiation Oncology clinics.

During the initial conversation between the investigator/research staff and the patient, the patient may be asked to provide certain health information that is necessary to the recruitment and enrollment process. The investigator/research staff may also review portions of their medical records at MSKCC in order to further assess eligibility. They will use the information provided by the patient and/or medical record to confirm that the patient is eligible and to contact the patient regarding study enrollment. If the patient turns out to be ineligible for the research study, the research staff will destroy all information collected on the patient during the initial conversation and medical records review, except for any information that must be maintained for screening log purposes.

In most cases, the initial contact with the prospective subject will be conducted either by the treatment team, investigator or the research staff working in consultation with the treatment team. The recruitment process outlined presents no more than minimal risk to the privacy of the patients who are screened and minimal PHI will be maintained as part of a screening log. For these reasons, we seek a (partial) limited waiver of authorization for the purposes of (1) reviewing medical records to identify potential research subjects and obtain information relevant to the enrollment process; (2) conversing with patients regarding possible enrollment; (3) handling of PHI contained within those records and provided by the potential subjects; and (4) maintaining information in a screening log of patients approached.

As participating in this protocol is not intended to provide any clinical benefit to the patient, patients will receive a stipend for their time. At the completion of their study participation, patients will receive a check for up to \$200, which is \$100 per completed FMISO scan session. If the patient does not complete both scan sessions, the stipend which they receive will be prorated for the number of sessions completed.

## **8.0 PRETREATMENT EVALUATION**

Patients must have the following tests or procedures prior to receiving any protocol scans.

- Histological confirmation of Non-Small Cell Lung Cancer at MSKCC
- Review of medical history and current medications
- Physical examination
- Pregnancy test for women of childbearing potential
- Standard clinical scans:
  - $^{18}\text{F}$ -FDG PET Scan performed at MSKCC
  - CT scan of the chest

## **9.0 TREATMENT/INTERVENTION PLAN**

Patients will be monitored by a member of the nuclear medicine staff before, during and through the completion of their imaging studies.

### **9.1 $^{18}\text{F}$ -FDG PET/CT:**

In patients who have consented to this study prior to their baseline  $^{18}\text{F}$ -FDG PET scan, 4D-CT (10 mA)/free breathing PET and breath hold CT(10 mA)/PET images will be acquired over one field-of-view encompassing the lesion in the  $^{18}\text{F}$ -FDG PET/CT scan in order to assess the improvement in the prognostic value of  $^{18}\text{F}$ -FDG-PET/CT in lung cancer due to correction of breathing-induced artifacts in the PET/CT images. The PET/CT acquisition will be assisted by an in-house developed respiratory tracking software and video camera to monitor the patients breathing motion, and then correct for breathing-induced artifacts in the PET/CT images. The patient breathing during all phases of the study will be monitored and recorded by the respiratory tracking device. Such respiratory tracking allows events captured by the PET scanner to be associated with different phases of the respiratory cycle. The baseline and follow-up  $^{18}\text{F}$ -FDG PET/CT scans for each individual patient should be performed on the same PET/CT scanner for consistency purpose. For patients receiving radiation therapy or concurrent chemo-RT, this research procedure will immediately follow the standard radiotherapy  $^{18}\text{F}$ -FDG PET/CT simulation protocol, with the patient in treatment position. This group will also receive a mid-treatment  $^{18}\text{F}$ -FDG PET/CT scan which will occur three weeks +/- 4 days after start of treatment of radiotherapy or the radiation portion of combined chemo-radiation. This mid-treatment  $^{18}\text{F}$ -FDG PET/CT is investigational. Only patients in Group 1 will participate in BH scans.

All research scans will be performed by the Nuclear Medicine team. For patients receiving radiation, all  $^{18}\text{F}$ -FDG PET/CT scans will be performed on the GE PET/CT scanner residing in the radiotherapy simulation suite. Otherwise, those scans will be performed on one of the GE PET/CT scanners residing in nuclear medicine.

## **9.2 F-FMISO PET/CT Scan Protocol:**

The first F-FMISO PET/CT scan will be performed within 14 days (+/- 5 days) after the baseline F-FDG scan, and before starting therapy. Dynamic FMISO PET scans will be performed on one of the GE Discovery PET/CT scanners residing in the nuclear medicine department at MSKCC. The patient will be set up in treatment position with intra-venous lines for radiotracer injection and for venous blood sampling. One 370 MBq (10 mCi) +/- 10% dose of F-FMISO will be injected as a bolus, and the dynamic scan initiated coincident with the injection.

Dynamic F-FMISO PET data will be acquired in List Mode and reconstructed in time frames that display the kinetics of tumor uptake. The total duration of the study is approximately 3 hours. The patient is injected in the PET scanning position on the couch and PET data acquired from 0-40 min. The patient is then allowed to return to the waiting room and rest. There are two further scan segments at approximately 90 min and 180 min post injection each of 10-minute duration. The total PET scan time within the 3 hour imaging session is therefore only 60 minutes. No further radioactivity will be injected for the 2nd and 3rd PET scan segments. In all three sessions of the dynamic PET study, the patient's breathing signal will be recorded simultaneously using the in-house developed tracking described previously. The respiratory signal will be used to retrospectively identify those PET events that occurred at end-expiration. Those events will be selected retrospectively to generate a dynamic PET data set corresponding to end-expiration (BH-dyn PET), motion-free PET images.

In each of the three dynamic sessions, a 4D-CT (10mA) scan and a BH-CT (10mA) scan (at end-expiration) of a 15cm segment of the body (the field of view of the PET scanner) will be performed with the tumor at the field center. These images will be used for both attenuation correction and registration of the serial image set, for the free-breathing and BH PET dynamic data sets respectively.

To further facilitate patient image registration, external fiducial markers may be placed on the patient's thorax.

A second set of three dynamic F-FMISO scans will be performed following the same sequence as outlined above for the baseline dynamic F-FMISO study, at 2 to 3 weeks (+/- 4 days) post-initiation of therapy.

To ensure patient safety, vital signs and toxicity assessments will be performed immediately after each scan session. Additionally, approximately 24 hours (or on the next business day) after the completion of each scan session, a toxicity assessment will be completed via a telephone followup.

Only patients in Group 1 will participate in BH scans.

## **9.3 Pharmacokinetic Modeling of F-FMISO PET:**

The dynamic data of the F-FMISO radiotracer in the tumor must be supplemented by clearance data from the blood. Blood samples may be taken at pre-designated times during the F-FMISO PET scan. If the PET images contain the heart within the field of view, one IV blood sample (about 1-2 ml) will be drawn at 30-40 minutes post F-FMISO injection. If the heart is not within the PET FOV, a maximum of 9 IV blood samples (about 1-2 ml each) may be obtained at approximately the following time points: 1, 2, 3, 4, 5, 15, 30, 90 and 180 minutes post injection. A separate IV line (other than the one used for FMISO injection) will be used to draw the blood. These samples will be weighed and counted for the purpose of determining the blood clearance kinetics and the tumor input function.

Compartmental kinetic analysis of the dynamic  $^{18}\text{F}$ -FMISO PET images will be conducted using the blood clearance time activity curve as input function to the  $^{18}\text{F}$ -FMISO compartmental model. The kinetic rate constants  $k_1$ ,  $k_2$ , and  $k_3$  (trapping rate) will be deduced. As a first approximation, hypoxic sub-regions within the tumor will be defined based on a  $k_3 > 0.1$ . We will then re-assess this  $k_3$  threshold based on results from the first 12 patients.

The same kinetic analysis will be repeated for the 2nd baseline  $^{18}\text{F}$ -FMISO study. The kinetic rate constants from the first and second  $^{18}\text{F}$ -FMISO studies will be compared, as well as the geographic positions of the hypoxic sub-volumes within the tumor between the first and second scans.

#### **9.4 Simultaneous $^{18}\text{F}$ -FDG/ $^{18}\text{F}$ -FMISO PET/CT Scan Protocol:**

[figure not shown]
Simultaneous Dynamic PET  $^{18}\text{F}$ MISO/ $^{18}\text{F}$ DG scan will be performed at least one day after the sole baseline  $^{18}\text{F}$ MISO PET/CT, but preceding chemo- or radiation therapies. Dynamic PET/CT data will be acquired over the same single FOV as for the sole baseline  $^{18}\text{F}$ MISO PET/CT described above. CT images will be acquired for PET attenuation correction purpose. Imaging will start simultaneously with the intravenous bolus injection of  $^{18}\text{F}$ -FMISO (8 mCi +/- 10%). PET data will be acquired in list mode (LM). The dynamic acquisition will last for up to a total of 120 min. 8 mCi (+/- 10%) of  $^{18}\text{F}$ DG will be injected intravenously 45 min +/- 15 min after the  $^{18}\text{F}$ -FMISO injection, and without interruption of the dynamic PET acquisition. One additional 10 min dynamic PET scan will be performed at 180 min post-FMISO injection. If the patient cannot tolerate the length of the first imaging session, an additional 10 min dynamic PET scan may be performed at 90 min +/- 10 min. Blood samples may be withdrawn following the same protocol as for the sole FMISO dynamic study described above.

For each of the imaging sessions a 4DCT at 10mA and a CT-BH (40mA and 1-mA for the first session and the subsequent sessions respectively) will be performed for attenuation correction,

All PET and CT data will be acquired and recorded in a secure patient database. During all imaging sessions, patients will be immobilized in RT alpha cradle if available and tolerable.

#### **9.5 Pharmacokinetic Modeling of Simultaneous $^{18}\text{F}$ -FDG/ $^{18}\text{F}$ -FMISO PET:**

We will perform compartmental analysis of the combined  $^{18}\text{F}$ -FMISO/ $^{18}\text{F}$ -FDG tumor uptake profiles obtained from dynamic PET images. The individual  $^{18}\text{F}$ -FMISO and  $^{18}\text{F}$ -FDG input functions will be derived from the drawn blood samples during the dynamic PET study, using Thin Layer Chromatography (TLC), and based on methodology we have previously developed. We have previously shown the feasibility of this technique to uncouple  $^8\text{F}$  based radiotracers,  $^{18}\text{F}$ -FMISO and  $^{18}\text{F}$ -FLT. We will use the same technique here to uncouple the FMISO/FDG fractions in the blood. The tumor combined FMISO/FDG Time Activity Curve (TAC), will be determined from the dynamic PET image set, and then the  $^{18}\text{F}$ MISO and  $^{18}\text{F}$ DG respective output functions will uncoupled from the combined TAC. Finally, compartmental analysis will be carried out for the FMISO and FDG respective output functions. The kinetic parameters  $V_{\square\square\square 1}$ ,  $k_2$ ,  $k_3$ , and  $k_4$  (for  $^{18}\text{FDG}$ ) will be calculated for the FMISO and FDG signals respectively. The procedure for carrying out compartmental analysis of FMISO and FDG dynamic PET with both radiotracers imaged within the same PET imaging session is shown in diagram 3.

- TLC: Thin Layer Tomography
- IF: Input Function
- TAC: Time Activity Curve
- CA: Compartmental Analysis
- KRC: Kinetic Rate Constant
- Sim: Radiotherapy Simulation

Diagram 3.

## 10.0 EVALUATION DURING TREATMENT/INTERVENTION

There will be no specific monitoring after the studies. All patients will be evaluated according to the standard of care for their lung cancer. Their imaging studies performed as part of standard of care every 3-4 months and their vital status will be periodically monitored for 3 years following treatment for the progression free survival and overall survival analyses.

	Day 0  BH F-FDG  PET/CT	F-FMISO1  (within 14 +/- 5 days after the baseline  F-FDG scan, and before starting therapy)	Mid Treatment Scans		Follow up
			F-FMISO2  Within occur two weeks +/- 4 days post initiation of therapy	F-FDG  (FDG: 3 to 4 weeks +/- 4 days post-initiation of therapy)	
Informed consent	X				
Review of your history and medication	X				
Physical exam	X				
Vital signs	X	X			
Standard clinical  F-FDG PET/CT scan	X		X		
 F-FMISO tracer injection		X 	X 	X	
Research PET scans	X	X	X	X	
Research blood draws		X	X		
Review of medical record for PFS and OS					X
Standard clinical CT of the chest					X 
Vital signs and Toxicity assessment 		X	X		

Table 1. Group 1: FMISO 2 Mid-Treatment Group Study Outline

	Day 0  F-FDG PET/CT	F-FMISO1  (within 14 +/- 5 days after the baseline  F-FDG scan, and before starting therapy)	Simultaneous F-FDG/F-FMISO 2  (at least one day after the first  F-FMISO scan but before starting therapy. This must also be within 14 +/- 5 days after baseline FDG scan)	Optional Mid Treatment F-FDG  (3 weeks +/- 4 days after RT)	Follow up
Informed consent	X				
Review of your history and medication	X				
Physical exam	X				
Vital signs	X	X			
Standard clinical  F-FDG PET/CT scan	X		X		
 F-FMISO tracer injection		X 	X 	X	
Research PET scans	X	X	X	X	
Research blood draws		X	X	X	
Review of medical record for PFS and OS					X
Standard clinical CT of the chest					X 
Vital signs and Toxicity assessment 		X			

Table 2. Group 2: Simultaneous FDG and FMISO group study outline

1. The F-FMISO and the simultaneous F-FDG/F-FMISO studies on each day will be performed in up to three separate imaging sessions, as was described earlier.
2. Vital signs and toxicity assessments will be performed immediately after each FMISO scan session. Additionally, approximately 24 hours (or on the next business day) after the completion of each scan session, a toxicity assessment will be completed via a telephone followup.
3. CT of the chest will be performed every 3 to 4 months from the completion of treatment for 3 years as per standard clinical care.

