- Perform a mid-treatment F-FDG PET/CT scan in a group of twenty five patients, undergoing RT or concurrent chemo-RT. This scan will occur two to three weeks +/- 4 days after start of treatment of radiotherapy or the radiation portion of combined chemo-radiation. F-FDG PET/CT scans will be performed in both Free-Breathing (FB) and Breath-Hold (BH) modes. The predictive value of F-FDG, based on the change in lesion SUVpeak between baseline and the 3-week mid-treatment

scan and following the PERCIST criteria, will be assessed using both the FB, and the BH, image sets independently. Results deduced from the FB and BH data sets will be compared and correlated with outcome.

- **Group 2: Combined  $^{18}\text{F}$ -FMISO/ $^{18}\text{F}$ -FDG baseline PET/CT:** In a group of 5 patients, two PET radiotracers  $^{18}\text{F}$ -FMISO and  $^{18}\text{F}$ -FDG will be injected sequentially into the patient. Since all PET radiotracers emit the same 511 keV coincidence photons, it is not possible to discriminate events from these different radiotracers. However, by conducting a dynamic PET/CT scan with staggered  $^{18}\text{F}$ -FMISO and  $^{18}\text{F}$ -FDG injections (45min +/- 15min apart), the kinetic profiles should provide sufficient information to allow signals from the two radiotracers to be clearly separated. This sequential  $^{18}\text{F}$ -FMISO /  $^{18}\text{F}$ -FDG study will be performed at least one day after the sole FMISO1 radiotracer baseline PET/CT scan, and prior to the initiation of therapy. The  $^{18}\text{F}$ -FMISO and  $^{18}\text{F}$ -FDG individual signals will be deduced from the combined dynamic PET images by means of kinetic modeling, and the corresponding radiotracers entrapments within the tumor will be determined. The accuracy of the  $^{18}\text{F}$ -FMISO signal extraction from the combined one in the staggered  $^{18}\text{F}$ -FMISO/ $^{18}\text{F}$ -FDG dynamic PET/CT study will be assessed by comparison to that deduced from the sole FMISO1 study (Diagram 2).

[figure not shown]

Diagram 1. Combined  $^{18}\text{F}$ -FMISO/ $^{18}\text{F}$ -FDG baseline PET/CT

[figure not shown]

Diagram 2. Group 2: Sequential FDG and FMISO treatment group

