### 11.2.2 $^{18}\text{F}$ -FMISO Production

$^{18}\text{F}$ -fluoride is produced by the Memorial Sloan-Kettering Cancer Center cyclotron by proton irradiation of an enriched O-18 water target in a small-volume titanium chamber.  $^{18}\text{F}$ - FMISO is prepared at an approximate specific activity of  $2.5 \times 10^7 \text{ MBq}/\text{mmol}$  at production time. Patients will be injected with a maximum of  $10 \pm 10\%$  mCi of  $^{18}\text{F}$ -FMISO on each of the 2  $^{18}\text{F}$ -FMISO scan days.

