### 11.2.3 Dosimetry Estimates for $^{18}\text{F}$ -FMISO

Bio-distribution data has been obtained for 25 patients at the University of Washington, and dosimetry was performed. Table 4 below summarizes normal organ doses due to  $^{18}\text{F}$ - FMISO administration.

F18-FMISO Patient Dosimetry			
Target Organ	Absorbed Doses		
	Median Dose (rad/mCi)	2.51 rad (*) + Dose (rad) per 10mCi FMISO	2x2.51 rad (*) + Dose (rad) per 2x10mCi FMISO
Adrenals	0.0614	0.614	1.228
Brain	0.0318	0.318	0.636
Breasts	0.0455	0.455	0.91
Heart Wall	0.0685	3.195	6.39
Stomach	0.0466	0.466	0.932
Kidney	0.0581	0.581	1.162
Liver	0.0677	0.677	1.354
Lungs	0.0366	2.876	5.752
Muscle	0.0525	0.525	1.05
Ovaries	0.0651	0.651	1.302
Red Marrow	0.0403	2.913	5.826
Spleen	0.0603	0.603	1.206
Thyroid	0.0559	0.559	1.118
Eye Lens	0.057	0.57	1.14
Total Body	0.0466	0.466	0.932
Urinary Bladder Wall			
45 min Voiding Interval	0.0291	0.291	0.582
1 hr Voiding Interval	0.0389	0.389	0.778
1.5 hrs Voiding Interval	0.0583	0.583	1.166
2 hr Voiding Interval	0.0777	0.777	1.554
Uterus	0.0677	0.677	1.354
Effective Dose Equivalent (rem)	0.0481	0.481	0.962

Table 4.

The organ receiving highest radiation dose from the two  $^{18}\text{F}$ -FMISO scans is the heart wall (  $2 \times 0.685 \text{ rad}$  ). Additional doses from 6 BH-CT scans (3 BH-CT per  $^{18}\text{F}$ -FMISO study) of  $0.396 \text{ rad}$  ( $6 \times 0.066 \text{ rad}$  ), and six 4D-CT scans (avg CT) (three 4D-CT per  $^{18}\text{F}$ -FMISO study) of  $4.626 \text{ rad}$  ( $6 \times 0.771 \text{ rad}$  ) for a total of  $2.51 \text{ rad}$  per  $^{18}\text{F}$ -FMISO study or  $5.02 \text{ rad}$  for both  $^{18}\text{F}$ -FMISO studies.

FMISO studies, will be delivered to the patient bringing the total radiation dose to the heart wall to 6.39 rad.

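### Table 1 marks an FMISO injection at the mid-treatment FDG visit, against the text and the two-injection dosimetry; Table 2 leaves the tracer at that visit unclear

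*Combined protocol and SAP*

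**What the plan says.** **Schedule tables (10.0).** In Table 1 the row "F-FMISO tracer injection" is marked under FMISO1, FMISO2 and the mid-treatment FDG column. In Table 2 it is marked under FMISO1, the simultaneous FDG/FMISO visit and the optional mid-treatment FDG column. The row "Vital signs and Toxicity assessment" is marked at both FMISO columns in Table 1, but only at FMISO1 in Table 2.

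**Text on the mid-treatment FDG visit.** The 1.0 Schema, 9.1 and 11.1.1 describe one investigational FDG scan and mention no FMISO. Its endpoint is the change in lesion SUVpeak from baseline (1.0 Schema).

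**Text on the number of FMISO injections.** The sentence in 11.2.2 that begins "Patients will be injected with a maximum of" sets the activity for each of two scan days, and Table 4 computes dose for 2 x 10 mCi. For dual-study patients, 2.0 makes a mid-treatment FMISO optional, and 11.2.5 includes a follow-up FMISO study in their total.

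**Text on separating the tracers.** Because both emit the same photons, the Schema says "it is not possible to discriminate events from these different radiotracers". It then proposes a staggered dynamic acquisition to separate them in Group 2.

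**Text on safety checks.** Sections 9.2 and 11.0 say that "vital signs and toxicity assessments will be performed immediately after each scan session". Footnote 2 to the tables reads "Vital signs and toxicity assessments will be performed immediately after each FMISO scan session" and adds a telephone check at about 24 hours.

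**The concern.** The schedule tables are what staff work from on the day. If Table 1 is followed as printed, a Group 1 patient receives a third FMISO injection that the text does not describe and Table 4 does not count. If it is given on the day of the FDG scan, its signal enters an SUVpeak that is meant to measure FDG alone. Extra uptake at mid-treatment, with none at baseline, makes the fall in SUVpeak look smaller than it was and so understates response. The separation method in 9.5 needs a dynamic acquisition and chromatography of blood samples. The mid-treatment FDG scan is described as free-breathing and breath-hold images giving SUVpeak, and Table 1 marks no blood draw in that column, so the bias could not be removed afterwards.

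**Working it through.** **1. Marks against columns.** Table 1 has three injection marks and only two FMISO columns. Misreading column positions could move a mark but would not create a third. In both tables the disputed mark lacks footnote 1, which describes the FMISO imaging sessions.

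In Table 2 the disputed column also marks research blood draws, which 9.3 and 9.4 describe only for FMISO and dual studies. Table 2 has no separate column for the optional mid-treatment FMISO of section 2.0. That visit could therefore be FDG, the optional FMISO, or both.

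**2. The plan's own doses (heart wall).** Inputs: FMISO 0.0685 rad/mCi and CT 2.51 rad per FMISO study (11.2.3); FDG 0.25 rad/mCi and CT 0.903 + 0.837 rad (Table 3); dual-study CT 0.198 + 2.313 rad (11.2.4). Section 9.2 gives "One 370 MBq (10 mCi) +/- 10% dose of" FMISO per sole study.
- One FMISO study: 10 x 0.0685 + 2.51 = 3.195 rad. Two: 6.39 rad, which matches "bringing the total radiation dose to the heart wall to 6.39 rad".
- Dual study: 8 x 0.25 + 8 x 0.0685 + 2.511 = 5.059 rad (matches).
- FDG: 12 x 0.25 + 0.903 + 0.837 = 4.74 rad (matches).
- Table 6: 4.74 + 6.39 + 5.059 = 16.189 rad (matches). FMISO activity covered: 10 + 10 + 8 = 28 mCi.

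**3. Group 1 with Table 1 read literally** (10 mCi assumed for the third injection, because the table gives no activity).
- FMISO: 3 x 10 = 30 mCi against 20 (33 against 22 at +10%).
- FMISO heart-wall dose, tracer only: 6.39 + 0.685 = 7.075 rad.
- FMISO heart-wall dose, full study with CTs: 3 x 3.195 = 9.585 rad.
- With FDG (+ 4.74): 11.815 to 14.325 rad, against 11.13 rad for two FMISO studies.

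**4. Group 2 with Table 2 read literally** (same assumption).
- FMISO: 10 + 8 + 10 = 28 mCi, the amount that Table 6 covers.
- Heart without the third injection: 3.195 + 5.059 + 4.74 = 12.994 rad.
- With it: 12.994 + 0.685 = 13.679 rad (tracer only) to 12.994 + 3.195 = 16.189 rad (full study), at or below Table 6.
- Table 6 is passed only if a separate optional FMISO study is done as well: 38 mCi, and 16.189 + 0.685 = 16.874 rad to 16.189 + 3.195 = 19.384 rad.

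**5. Can same-day FMISO arise from the text alone?** Days are counted from the start of radiotherapy, on the assumption that all windows share that origin.
- FMISO2: days 10-18 (Schema, Table 1) or 10-25 (9.2).
- FDG: days 10-25 (Schema), 17-25 (9.1) or 17-32 (Table 1).

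Every pairing overlaps, if only on days 17-18. At baseline FMISO normally follows FDG by at least one day; no gap is stated mid-treatment.

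**6. Effect on SUVpeak.** Fractional inflation = (10 x FMISO SUV) / (12 x FDG SUV). The activities come from 9.2 and Table 3. The SUV ranges, 1.5-2.5 for FMISO and 4-8 for FDG, are assumptions.
- Low: 15 / 96 = 0.156. High: 25 / 48 = 0.521.
- Example: a true fall from 8 to 4 (50%) reads as 8 to 4 + 1.25 = 5.25 (34%) or 8 to 4 + 2.08 = 6.08 (24%).
- If FMISO is instead given 4 hours before FDG (assumed; F-18 half-life taken as 109.8 min), the decay factor is exp(-ln2 x 240/109.8) = 0.22, and inflation is 3-11%.

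**The case against.** The strongest reply is that this is a clerical slip with little chance of harm. The disputed Table 1 mark has no footnote 1, its column has no blood draw or toxicity mark, the column is headed FDG, the text describes FDG only, and the study runs at a single institution (4.1). A row-label error is the natural reading. All of this stands. It makes the risk conditional, but the contradiction remains in an operative schedule.

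For Table 2 the mark may simply be the optional mid-treatment FMISO of section 2.0 under an incomplete column header. That cannot be excluded, and it is why the finding there is ambiguity.

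A reader might also infer three stronger things that the documents do not support:
- **The dual-injection session has no safety check.** Table 2's injection mark at that visit carries footnote 2, which requires the check, as do 9.2 and 11.0. Only the cell in the toxicity row is blank, and a blank cell can neither add exposure nor bias SUVpeak.
- **Group 2 exceeds its stated exposure.** Table 6 already covers 28 mCi and 16.189 rad. That activity does not fit the two scan days of 11.2.2, but Table 6 itself has the same mismatch.
- **The FDG mark for mid-treatment is misplaced under FMISO2 in Table 1.** That row is for standard clinical FDG, whereas the mid-treatment scan is investigational and its research-scan mark is in its own column. A column shift in that row cannot be excluded.

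Finally, the FDG analysis is declared exploratory (14.0), and the inflation rests on assumed SUVs. Both limit the weight of the point.

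**Conclusion.** The point holds for Table 1: its FMISO mark at the mid-treatment FDG visit contradicts the FDG-only text and the two-injection count. Followed literally, with 10 mCi assumed for the extra injection, it means 10 mCi more FMISO in Group 1, and 0.685 rad (tracer only) to 3.195 rad (full study) more to the heart wall. The direction of the SUVpeak bias follows from the protocol's own statement about the tracers. Its size does not: 16-52% for co-injection is illustrative, and a longer lead shrinks it. For Table 2 the conclusion is only that the tracer at the optional visit cannot be determined. The toxicity cell is a minor inconsistency. The documents do not show that any patient would in fact receive the extra injection.

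**What to change.** 1. Reconcile Tables 1 and 2 with sections 1.0, 2.0, 9.1, 9.2 and 11.2.2 and with Tables 4 and 6, so that all of them name the same tracer or tracers at each mid-treatment visit and the dosimetry counts the same injections. Which entry is correct is for the sponsor to decide.
2. Make the Table 2 toxicity row agree with footnote 2.
3. Add one sentence to the FDG analysis in 14.0: FDG SUVpeak is taken only from scans with no FMISO injected the same day, and same-day cases are logged as non-evaluable for that endpoint. This is useful even if the mark is clerical, because the windows overlap with no stated gap.

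The cost is a correction to two tables and one sentence, with no added procedure. The small downside is the possible loss of a few evaluable FDG scans.
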